## 3.0 STUDY POPULATION

### 3.1 Inclusion Criteria

1. Histologically or cytologically confirmed sarcoma (including extremity), thoracic cancer (including esophageal), abdominal cancer, or pelvic cancer.

2. Planning to undergo palliative radiotherapy to a lesion  $\geq$  4.5 cm as measured with radiographic imaging or with calipers by clinical exam.
3. ECOG performance status  $\leq$  2
4. At least 18 years of age.
5. Radiotherapy is known to be teratogenic. For this reason, women of childbearing potential and men must agree to use adequate contraception (hormonal or barrier method of birth control, abstinence) prior to study entry and for the duration of study participation. Should a woman become pregnant or suspect she is pregnant while participating in this study, she must inform her treating physician immediately. Men treated or enrolled on this protocol must also agree to use adequate contraception prior to the study, for the duration of the study, and 6 months after completion of the study
6. Ability to understand and willingness to sign an IRB approved written informed consent document.

### **3.2 Exclusion Criteria**

1. Prior high-dose radiotherapy that overlaps with any planned site of protocol radiotherapy. Patients where the Lattice SBRT fields may overlap with the low dose ( $<10$  Gy) region of prior radiotherapy treatments are eligible and may be treated if this is determined to be safe by the treating physician.
2. Patients with tumors in need of urgent surgical intervention, such as life-threatening bleeding or those at high risk for pathologic fracture.
3. Currently receiving any cytotoxic cancer therapy regimens or VEGF inhibitors that will overlap with the Lattice SBRT administration.
  - a. Cytotoxic chemotherapy and VEGF inhibitors prior to radiotherapy or planned after radiotherapy delivery are allowed at the discretion of the treating radiation oncologist. This includes continuing a treatment plan which was initiated prior to the start of radiotherapy. A 2-week washout is recommended, but not required.
4. Pregnant. Women of childbearing potential must have a negative pregnancy test within 20 days of study entry.
5. Patients with HIV are eligible unless their CD4+ T-cell counts are  $< 350$  cells/ $\mu$ L or they have a history of AIDS-defining opportunistic infection within the 12 months prior to registration. Concurrent treatment with effective ART according to DHHS treatment guidelines is recommended. Recommend exclusion of specific ART agents based on predicted drug-drug interactions (i.e. for sensitive CYP3A4 substrates, concurrent strong CYP3A4 inhibitors (ritonavir and cobicistat) or inducers (efavirenz) should be contraindicated).

### **3.3 Inclusion of Women and Minorities**

Both men and women and members of all races and ethnic groups are eligible for this trial.

## **4.0 REGISTRATION PROCEDURES**

**Patients must not start any protocol intervention prior to registration through the Siteman Cancer Center.**

The following steps must be taken before registering patients to this study:

1. Confirmation of patient eligibility
2. Registration of patient in the Siteman Cancer Center database
3. Assignment of unique patient number (UPN)

### **4.1 Confirmation of Patient Eligibility**

Confirm patient eligibility by collecting the information listed below:

1. The registering MD's name
2. Patient's race, sex, and DOB
3. Three letters (or two letters and a dash) for the patient's initials
4. Copy of signed consent form
5. Completed eligibility checklist, signed and dated by a member of the study team
6. Copy of appropriate source documentation confirming patient eligibility

### **4.2 Patient Registration in the Siteman Cancer Center OnCore Database**

All patients must be registered through the Siteman Cancer Center OnCore database.

### **4.3 Assignment of UPN**

Each patient will be identified with a unique patient number (UPN) for this study. All data will be recorded with this identification number on the appropriate CRFs.

### **4.4 Screen Failures**

Screen failures are defined as participants who consent to participate in the clinical trial but are not entered in the study. A minimal set of screen failure information is required to ensure transparent reporting of screen failure participants, to meet the Consolidated Standards of Reporting Trials (CONSORT) publishing requirements and to respond to queries from regulatory authorities. Minimal information includes demography, screen failure details, eligibility criteria, and any serious adverse event (if applicable).

## **4.5 Strategies for Recruitment and Retention**

Our institution sees a high volume of patients that are referred for palliative radiotherapy.

The primary source of patients who are eligible for this study will be radiation oncologists within our department. The most likely service lines to see patients with large tumors in need of palliative radiotherapy are sarcoma, thorax (i.e. lung cancer), gastrointestinal, gynecologic (pelvic), and palliative. [name] (sarcoma, thorax, gastrointestinal) is the PI, and the other service line chiefs are enthusiastic about this trial and are listed as co-investigators: [name] (Thorax), [name] (Gastrointestinal), [name] (Gynecologic), [name] (Palliative). Additionally, a full-time research coordinator will be assigned to this study who will assist in screening patients who are referred to our department for palliative radiotherapy for a large tumor.

With the current rate of patients in need of palliative radiotherapy presenting to our department, we anticipate approximately 100 patients per year will be eligible for this protocol. A conservative estimate is that 50% of these patients will consent to participate in this study. This yields an estimated accrual of 50 patients per year. We anticipate that we will enroll 67 patients of all genders, races, and ethnicities. Given the hypofractionated course of therapy, 95% of patients should be able to complete therapy. We anticipate that we will accrue approximately 4 patients per month, therefore completing accrual in 15 months. Patients will be accrued from the outpatient clinics and inpatient hospitals of one U.S. site. Potential participants will be identified by our multidisciplinary team physicians and discussed in tumor board.

## **5.0 TREATMENT PLAN**

### **5.1 Study Intervention Description**

Consenting and eligible patients will undergo Lattice SBRT prescribed to a dose of 20 Gy in 5 fractions with a simultaneous integrated boost of 66.7 Gy in 5 fractions. As long as radiotherapy fields do not overlap, treatment of up to 4 other tumor sites are allowed. Lattice SBRT is required for all tumor sites  $\geq 4.5$  cm. Lattice SBRT fractions will be delivered every other day. For sites  $< 4.5$  cm, other planning techniques may be used (i.e. 3D conformal or SBRT). Following radiotherapy, patients will be evaluated for toxicity at 30 days, 3 months, 6 months, and 12 months.

### **5.2 Risk Designation for Tumor Lysis Syndrome (TLS)**

While it is rare with solid tumor malignancies, the risk of tumor lysis syndrome (TLS) may be elevated with spatially fractionated radiotherapy. Patients at high-risk for or complications from TLS are those meeting ANY of the following criteria:

- Radiosensitive histologies including lymphoma, breast cancer, small cell carcinoma, neuroblastoma, germ cell tumors, medulloblastoma, myxoid

- liposarcoma, undifferentiated pleomorphic sarcoma, angiosarcoma, synovial sarcoma, and squamous cell carcinomas of the head and neck, skin, or gynecological cancers (i.e. cervix, ovary)
- Patients who have received or plan to receive systemic therapy within 2 weeks or less of starting or finishing Lattice SBRT
- Patients with a history of CKD stage III based on MDRD eGFR calculation, a history of cardiac arrhythmias, or seizures.
- Patients with LDH, uric acid, or potassium above the normal limit on pre-radiation evaluation.

### **5.3 Monitoring for TLS**

For all patients, assessments of hematologic and metabolic function such as a CBC and renal function panel (required to include assessments of uric acid, potassium, phosphorus, and calcium) will be collected at the following time points:

- No more than 1 week before treatment (including on the day of treatment)
- Immediately after radiotherapy completion (Fraction 5, day 0)
- At 48-72 hours after radiotherapy completion
- At 7 days (+/- 1 day) after radiotherapy completion

### **5.4 Pre-Radiation Evaluation**

- History and physical exam by team radiation oncologist
- Assessment of hematologic and metabolic function such as a CBC and renal function panel. This must include assessments of uric acid, potassium, phosphorus, and calcium.
- CT, PET/CT, or MRI of the chest, abdomen, and pelvis
- Completion of baseline NRS pain score (if applicable), PRO-CTCAE, PROMIS Global, Physical Function, Pain Interference, Anxiety, and Depression questionnaires
- Peripheral blood collection.

### **5.5 Radiation Therapy**

Lattice SBRT must be used for at least one lesion 4.5 cm or greater. The prescription dose for Lattice SBRT is 20 Gy in 5 fractions with a SIB to 66.7 Gy in 5 fractions. For Lattice SBRT, patients must be treated with intensity modulated radiotherapy (IMRT) or volumetric modulated arc therapy (VMAT). Intensity modulated proton therapy (IMPT) is allowed.

For Lattice SBRT, each lesion should be treated no more frequently than every other day, but treatment of each lesion may be staggered so that the patient has radiotherapy daily. No more than 3 lesions should be treated on the same day.

For other lesions, a standard palliative regimen of 5 fractions or less is encouraged but not required, and lesions amenable to conventional SBRT may be treated as such as well.

Multiple Lattice radiotherapy plans delivered during the trial period may not overlap. Reirradiation of prior irradiated sites is not allowed.

### **5.5.1 Localization, Simulation, and Immobilization**

Simulation and treatment position will be determined by the treating radiation oncologist and team. Patients should be optimally positioned for stereotactic body radiation therapy with alpha cradles, aquaplast masks, or other methods of immobilization. The use of devices to alter dose distributions, such as bolus or lead shields, are allowed. Use of techniques to control and/or accommodate tumor motion may also be employed in constructing the planning target volume (PTV).

A treatment planning CT scan or MRI in the treatment position will be required to define the PTV. The extent of the CT scan will be determined at the discretion of the treating physician. A CT scan slice thickness of  $\leq 5$  mm should be employed.

### **5.5.2 Treatment Planning/Target Volumes**

The definitions for the GTV, PTV and normal structures used in this protocol generally conform to the 1993 ICRU report #50 titled Prescribing, Recording and Reporting Photon Beam Therapy.

#### **5.5.2.1 Target Volumes and Normal Structures**

##### Target Volumes

[figure not shown]
*Gross Tumor Volume (GTV):* Contour using all available clinical and radiographic information. Fusion of other diagnostic imaging to delineate the GTV is allowed. Construction of an iGTV using 4DCT imaging is allowed. For boney lesions of the spine, the entire involved vertebral body may be included in the GTV.

*Planning Target Volume 2000 cGy (PTV\_2000):* Represents a geometric expansion of the GTV (or iGTV) of up to 1.0 cm. The PTV should be reduced as not to extend beyond the patient (i.e. in to air) and may be reduced as to not extend into skin (i.e. external contour contracted by 3-5 mm).

*GTV-5:* Represents a geometric contraction of 0.5 cm from the GTV, and is used for generation of the subsequent high-dose target.

*Planning Target Volume 6670 cGy (PTV\_6670):* Spheres with diameter 1.5 cm should be placed 6 cm apart as measured from center to center inside the GTV. The spheres should be placed to maximize the number of whole spheres within the GTV. There should be 3 cm between axial slices in which spheres are placed. Spheres extending outside of the GTV-5 structure will

be cropped, and the resultant spherical volume will represent the high-dose target of the PTV\_6670.

*A) Geometric representation of sphere placement. Yellow dots represent the 1.5 cm diameter PTV\_6670 target vertices, and dotted line vertices represent the transposed target vertices from adjacent planes. Axial planes where vertices are placed are separated by 3 cm in-plane. Within a plan, vertices are separated by 6 cm center to center (4.5 cm edge to edge) in orthogonal axes, and  $3\sqrt{2}$  cm along the diagonal. B) Axial CT slices of a pelvic tumor with the yellow outlined target vertices (PTV\_6670) in each plane, red GTV\_2000, and green PTV\_2000. Magenta arrows denote cropped vertices in PTV\_6670 that extend outside of the GTV\_2000. C) Dose distribution after VMAT planning for the pelvic tumor with accompanying dose color wash legend.*

**Normal structures:** Relevant normal structures and their dose constraints are described in the table below. Each normal structure should be contoured in its entirety.

### 5.5.2.2 Radiation Treatment Planning

CT-based planning with tissue inhomogeneity correction is required. Daily IGRT is required. Motion management strategies such as breath holding, respiratory gating, fluoroscopy, and MR-guided daily adaptive therapy are allowed.

### 5.5.2.3 Planning Objectives and Normal Tissue Constraints

The normal tissues in the table below are to be contoured in their entirety when present on the CT simulation scan.

The following organs and doses are guidelines for the radiation treatment plan. **Organ at risk tolerance levels cannot be exceeded.** Under coverage of PTV targets in order to meet OAR constraints is allowed.

- PTV\_2000: at least 95% should be covered by 20 Gy. Keeping Dmax within the PTV\_2000 and outside the PTV\_6670 to less than 24 Gy is recommended but not required.
- PTV\_6670: at least 95% should be covered by 66.7 Gy. A Dmin of at least 60 Gy within vPTV is recommended.

Serial Tissue	Max point* dose (Gy)
Optic pathway	25
Cochlea	22
Brainstem (excluding medulla)	31
Spinal cord and medulla	28
Cauda equina	31.5
Sacral plexus	32
Esophagus	35
Brachial plexus	32.5
Heart/pericardium	38
Great vessels	53
Trachea and large bronchus	40
Bronchi	33
Skin	38.5
Stomach	35
Bile duct	41
Duodenum	26
Jejunum/ileum	32
Colon	40
Rectum	55
Ureter	45
Bladder wall	38

\*A point is defined as volume  $\leq 0.035$  cc)

Parallel Tissue	Critical Dose (Gy)	Critical Volume
Lungs - GTV	12.5	< 1500 cc
	13.5	< 1000 cc
		< 37%
Liver	21	< 700 cc
Renal cortex (bilateral)	28	< 200 cc
Renal cortex (single kidney)	14.5	< 130 cc
Femoral Heads (Right & Left)	30	<10 cc

### 5.5.3 Dose Specifications

For Lattice SBRT, the daily prescription dose will be 20 Gy to be delivered to the PTV\_2000 with a SIB of 66.7 Gy to be delivered to the PTV\_6670 over 5 fractions (4 Gy and 13.34 Gy to the PTV\_2000 and PTV\_6670 per day, respectively). All doses will be prescribed to the periphery of the PTVs. In general, the prescription isodose line (generally 93-98%) chosen should encompass at least 95% of the PTV. Under coverage of the PTV to meet dose constraints is allowed.

The maximum point dose, minimum point dose, and the mean dose to the PTV will also be reported.

#### **5.5.4 Technical Factors**

The guidelines for VMAT in this trial will conform to the policies set by the Advanced Technology Consortium (ATC) and the National Cancer Institute (NCI). Each of the target volumes and normal structures listed below must be delineated on each slice from the 3D planning CT in which that structure exists.

#### **5.5.5 Radiation Quality Assurance**

Radiation quality assurance will be evaluated by a Medical Physics team. Prior to treatment, plan quality will be assessed with an ion chamber and film-based dosimeters.

### **5.6 Patient-Reported Quality of Life Outcome and Toxicity Measures**

Symptom response and patient-reported quality of life will be measured using the pain numeric rating scale, PRO-CTCAE (abridged as indicated in Appendix D), PROMIS Global, Physical Function, Pain Interference, Anxiety, and Depression questionnaire at the following time points:

1. Within 2 weeks prior to the start of radiotherapy
2. Within 3 weeks after completion of radiotherapy
3. At 30 days after radiotherapy
4. At 90 days after radiotherapy
5. At 180 days after radiotherapy
6. At 360 days after radiotherapy

The patient reported outcomes measures will be conducted using a computer-assisted interview program and may be done in person before/after a routine office visit or over the phone at the preference of the study participant. Patient reported outcomes may also be collected online.

### **5.7 Acquisition of Blood for Research**

Refer to Section 8.0.

## **5.8 Definitions of Evaluability**

All patients enrolled on the study are evaluable for toxicity if they have received at least one fraction of radiation. Patients are evaluated from first receiving study treatment until 90 days after the conclusion of treatment or death. Participants who are consented but do not receive study treatment will be replaced.

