## PROTOCOL SUMMARY

Title:	A Trial of Palliative Lattice Stereotactic Body Radiotherapy (SBRT) for Patients with Sarcoma, Thoracic, Abdominal, and Pelvic Cancers
Study Description:	Lattice SBRT will be used to deliver palliative radiotherapy to large ( $\geq 4.5$ cm) tumors for patients with soft tissue sarcomas, thoracic cancers (including esophageal), abdominal, and pelvic cancers. The safety and efficacy of this approach will be assessed.
Objectives:	
Primary Objective:
 
 
1. To evaluate the efficacy and safety of 5-fraction palliative Lattice SBRT in patients with large lesions (<math>\geq 4.5</math> cm) who are planning to undergo palliative radiotherapy. This will be assessed with the co-primary endpoints of target lesion control at 6 months and rate of treatment-related severe toxicity within 6 months.
 
 
Secondary Objectives:
 
 
1. To assess the rate of treatment-related severe toxicity within 12 months of completion of treatment (i.e. late toxicity)
 
2. To assess patient reported toxicity with PRO-CTCAE
 
3. To assess patient-reported QoL with PROMIS
 
4. To assess patient-reported pain
 
 
Exploratory Objectives:
 
 
5. To evaluate blood for immune- and tumor damage-associated response with Lattice SBRT
 

Endpoints:	
Primary:
 
 
1. Rate of local control by RECIST at 6 months
 
2. Proportion of patients with treatment-related grade 3+ CTCAE v5.0 toxicity assessed within 6 months of completion of treatment
 
 
Secondary:
 
 
1. Proportion of patients with treatment-related grade 3+ CTCAE v5.0 toxicity at 12 months.
 
2. PRO-CTCAE assessment at baseline, post-treatment, 30 days, 3 months, 6 months, and 12 months.
 
3. PROMIS physical function, global health, anxiety, and depression assessment at baseline, post-treatment, 30 days, 3 months, 6 months, and 12 months.
 
4. Numeric Pain Scale at baseline, post-treatment, 30 days, 3 months, 6 months, and 12 months.
 
 
Exploratory: Peripheral blood immune-related biomarkers.

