### 11.2 Study Endpoints

The co-primary endpoints are rate of local control of the treated (i.e. target) lesion at 6 months, and proportion of patients with treatment related grade 3+ CTCAE v5.0 toxicity. Local control will be determined by RECIST 1.1 analysis of baseline compared with imaging at 6 months. Imaging may include CT scan, PET/CT, or MRI. It is strongly suggested that the same imaging modality is used between baseline and at every follow-up timepoint for staging of disease.

Importantly, there are limited available data to determine expected local control of large tumors after SBRT. Almost all studies have focused on tumors with average maximal diameter of only 5.5 cm corresponding to a tumor volume of approximately 87 cc. In such studies, local control rates are approximately 70-85%. In the pilot study of Lattice SBRT at Washington University, the median treated tumor volume was 435 cc (N=14). Likewise, these few studies of SBRT for large tumors report a grade 3+ toxicity rate of 5-25%, varying based on tumor location.

Due to the lack of a reliable historical comparison, the enrollment target was defined by clinical considerations as opposed to power calculations for comparison with a historical control. This study instead seeks to establish the expected local control rate at 6 months for patients with such large tumors treated with Lattice SBRT. After discussing with internal and external stakeholders, we determined that a clinically reasonable bound on local control at 6 months would be 15%. Approximately 47 patients would be required to determine local control with a 95% confidence interval of +/- 15%; 67 patients will be enrolled to get 47 evaluable patients. We anticipate that up to 30% of patients may not be evaluable for local control at 6 months and are accounting for this potential drop-out rate by enrolling 67 patients. This is because patients with very large tumors needing palliative radiotherapy often have short survival.

Likewise, the study seeks to establish the expected grade 3+ treatment related toxicity rate for treatment of large tumors with lattice SBRT. The treatment will be considered safe if the grade 3+ treatment related toxicity rate is less than 20%, which is in line with prior studies of SBRT of large tumors.

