### **11.4 Power Analysis and Sample Size**

Approximately 67 evaluable patients will be enrolled. The proposed sample size was chosen based on clinical considerations, to allow for establishment of an expected 6-month local control rate and treatment related grade 3+ CTCAE toxicity rate for treatment of very large tumors.

After discussing with internal and external stakeholders, we determined that a clinically reasonable bound on local control at 6 months would be 15%. Approximately 47 patients would be required to determine local control with a 95% confidence interval of +/- 15%. However, patients with large tumors needing Lattice SBRT are expected to have a short median survival. Based on our prior experience, we expect 20-30% of patients will complete Lattice SBRT but may be unevaluable for the primary endpoint. Enrolling 67 patients with an up to 30% drop out rate would ensure at least 47 evaluable patients to create our clinically acceptable 95% CI estimate for local control at 6 months.

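### The co-primary toxicity rate is a crude proportion with no censoring of patients lost alive before 6 months, so it leans towards a safe verdict by an amount the documents do not fix

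*Combined protocol and SAP*

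**What the plan says.** All references are to the combined protocol and SAP.

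- **Denominator.** Section 5.8: "All patients enrolled on the study are evaluable for toxicity if they have received at least one fraction of radiation". No minimum follow-up is attached.
- **Evaluation window.** The next sentence of 5.8 reads "Patients are evaluated from first receiving study treatment until 90 days after the conclusion of treatment or death".
- **Endpoint.** The Protocol Summary defines the second co-primary endpoint as "Proportion of patients with treatment-related grade 3+ CTCAE v5.0 toxicity assessed within 6 months of completion of treatment".
- **Decision rule.** Section 11.2: "The treatment will be considered safe if the grade 3+ treatment related toxicity rate is less than 20" per cent. No confidence bound is attached.
- **Analysis.** Section 11.3 plans only descriptive statistics for toxicity. It has no rule for censoring, competing events or missing follow-up.
- **Expected attrition.** Section 11.4: "we expect 20-30% of patients will complete Lattice SBRT but may be unevaluable for the primary endpoint". Section 11.2 is more specific: "We anticipate that up to 30% of patients may not be evaluable for local control at 6 months". It gives the reason: "This is because patients with very large tumors needing palliative radiotherapy often have short survival".
- **Another denominator.** The stopping boundary in 11.6 counts only patients with full follow-up.

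**The concern.** In a crude proportion, a patient who is in the denominator and has no recorded event is a non-event. Section 5.8 puts every patient with one fraction in the denominator, and nothing later removes or censors them. A patient lost alive at month 2 without a grade 3+ event is therefore credited with four event-free months that nobody observed. Unobserved time can hide events but cannot create them, so the error runs only towards a lower rate.

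The rate is compared with a fixed cut-off. With 67 treated patients, 13 events (19.4%) is safe and 14 (20.9%) is not. With one patient separating the two verdicts, modest under-counting can change the conclusion on a co-primary endpoint.

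**Working it through.** **1. The plan's own figures.** Section 11.4 states "Approximately 47 patients would be required to determine local control with a 95% confidence interval of +/- 15" per cent. The exact (Clopper-Pearson) interval has a maximum half-width of 0.151 at n = 46 and 0.149 at n = 47, so 47 reproduces. At 30% loss, 67 × 0.70 = 46.9, so 67 reproduces. This allowance was built for local control; the plan makes none for toxicity.

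**2. Passing count.** 0.20 × 67 = 13.4, so the treatment passes with at most 13 events.

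**3. Formula.** Let p be the true 6-month risk, d the share lost alive before 6 months, and f the fraction of those patients' events that occur before they leave. Patients who leave are assumed to have the same risk as the others.

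- Expected observed rate = p × [(1 − d) + d × f]
- Chance of a safe verdict = P(X ≤ 13), X binomial with n = 67 and that rate

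The documents give neither d nor f. I take p = 22% as an illustrative true rate just above the cut-off.

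**4. Even event timing and exit halfway (f = 0.5).**

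| d | Observed rate | P(safe) |
|---|---|---|
| 0 | 22.0% | 0.37 |
| 5% | 0.22 × 0.975 = 21.5% | 0.41 |
| 10% | 0.22 × 0.95 = 20.9% | 0.45 |
| 30% | 0.22 × 0.85 = 18.7% | 0.63 |

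**5. Range over f.** At f = 1 (all events precede exit) the rate stays at 22% and P(safe) at 0.37 for any d. At f = 0 (none captured), d = 5% gives 0.22 × 0.95 = 20.9% and 0.45. Likewise d = 10% gives 0.22 × 0.90 = 19.8% and 0.54, and d = 30% gives 0.22 × 0.70 = 15.4% and 0.86. The f = 0 figures are bounds, since events before exit are counted.

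**6. Deaths.** A patient who dies without toxicity has been observed until death. If every early exit is a death, the cumulative incidence with death as a competing event equals the crude proportion over all treated patients, so d = 0 in the table.

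**7. The other obvious denominator.** Counting only patients with an event or full 6-month follow-up keeps early leavers who had events and drops those who did not. With p = 18%, d = 30% and f = 0.5, the numerator is 0.18 × 0.85 = 0.153. The denominator is 0.70 + 0.30 × 0.18 × 0.5 = 0.727, and the ratio is 21.0%. A treatment with a true rate of 18% would on average fail.

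**8. Windows side by side.** Section 5.8 ends evaluation at 90 days, the Protocol Summary sets 6 months, and Section 7.0 tracks adverse events through 360 days. If the 90-day limit governed the co-primary endpoint, events between 90 days and 6 months would be missed in every patient, whatever the dropout.

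**The case against.** The strongest reply is that the plan nowhere says patients who leave early are toxicity-free, and nowhere gives a rate of missing toxicity follow-up. A reader might infer from 11.4 that 20-30% will lack a 6-month toxicity assessment. The documents do not support that: 11.2 ties the figure to local control, which needs a scan, and to short survival. Toxicity needs no scan. Section 5.12 allows follow-up by records review and telephone, Section 5.11 keeps patients who stop treatment early under follow-up, and Section 7.0 tracks events for 360 days. A reader might also infer that early deaths bias the rate. They do not when death is a competing event; wanting the risk among patients who survive the window is a different estimand. Finally, Section 2.0 describes the toxicity objective as acute and sub-acute. If most events come early, f is near 1 and little is lost.

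All of this stands, and it limits the size. It does not remove the gap. Counting a patient lost alive as a non-event needs no written rule; it follows from the one-fraction denominator and a plain proportion. Section 5.13 expects some losses to follow-up, and the plan does not say how they enter the co-primary result.

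**Conclusion.** The concern holds as a missing censoring rule with a known direction and an unknown, possibly small, size. For a true 22%, an assumed 5-10% lost alive halfway moves the observed rate to 21.5-20.9% and the chance of a safe verdict from 0.37 to 0.41-0.45. The shift to 18.7% and 0.63 requires all 30% to be lost alive, which the stated reason of short survival makes an upper bound for d rather than an expectation. These figures rest on even event timing, exit halfway and equal risk in those who leave. The bias is zero if all losses are deaths or all events precede exit.

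A reader might go further and require both the crude rate and the rate among patients with an event or full follow-up to be below 20%. That is not supported: the second rate is biased upward, so the double requirement would swap a possible lean towards safe for a built-in lean towards unsafe.

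**What to change.** - **Primary estimate.** In 11.3, estimate 6-month treatment-related grade 3+ toxicity by Aalen-Johansen cumulative incidence with a 95% confidence interval. Censor patients lost to follow-up at last contact and treat death without toxicity as a competing event. Apply the 20% criterion of 11.2 to this estimate. State the assumption that loss is unrelated to toxicity risk.
- **Sensitivity lines only.** Report the crude proportion, and the proportion among patients with an event or full 6-month follow-up, noting that the latter is biased upward. Do not require both to be below 20%.
- **Attrition.** Report deaths and losses alive before 6 months separately, so that the size of the correction is visible.
- **Reconcile.** Bring the 90-day window in 5.8 into line with the 6-month endpoint, and the 5.8 denominator with the full-follow-up denominator in 11.6, or state why they differ.

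The cost is SAP wording and one additional analysis. The toxicity, follow-up and death forms listed in 9.0 should supply the event, last-contact and death dates; confirm that all three are recorded. The reported rate may be slightly less favourable.
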